## Statistical Analysis

In this pilot study, thirty participants will be enrolled: 15 randomized to the intervention group, and 15 randomized to the control group with a goal of 10 participants completing the study in each group. Data gathered from this study will be used to complete sample size and power calculations for a larger randomized controlled trial. A sample size of 10 per group achieves 80% power to detect a difference of -0.02 (correlation coefficient) between the null hypothesis correlation of 0.0 and the alternative hypothesis correlation of 0.02 using a two-sided hypothesis test with an estimated standard deviation of 0.02 and with a significance level of 0.05 using a two-sided Wilcoxon test, assuming that the actual distribution is normal.

Collection of study data is focused on feasibility and gathering evidence to inform future studies, thus, all analyses are considered exploratory rather than confirmatory. Baseline characteristics will be summarized using descriptive measures, both overall, by gender, and by group, at baseline. The primary outcome of feasibility will be based on retention of participants at follow-up visits and description of tolerance of the active and inactive group in response to infusion. Follow-up treatment effect estimates at 9 months will be used in power calculations for future clinical trials. Secondary analyses will examine change in bone metrics between groups assessed by a Students t-test. The effect of changes in relevant co-variates such as lean mass, muscle function and nutrition status on study outcomes will be assessed. Regression models will be used to control for appropriate co-variates and further explore the effect of zoledronic acid on bone after bariatric surgery.

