## Protocol

### Summary

One in three adults in the United States suffers from obesity. Bariatric surgery is an increasingly utilized and effective treatment for obesity and obesity-related comorbidities, however, the massive weight loss associated with bariatric surgery adversely affects bone metabolism. Significant decreases in bone mineral density lead to an increased risk of fracture and subsequent reduction in physical function among bariatric surgery patients. Bisphosphonate medications, such as zoledronic acid, have been evaluated for safety and efficacy in combating bone loss in patients with osteoporosis, but their use in bariatric surgery induced bone loss has not been explored. The study's primary goal is to investigate whether bisphosphonate therapies are able to combat bone loss associated with surgical weight loss procedures. This research proposal is a 1-year, pilot randomized controlled trial involving 20 adult sleeve gastrectomy participants randomized to receive either a onetime zoledronic acid infusion or placebo. The hypothesis is that zoledronic acid, a standard treatment for low bone density, will be an effective intervention to reduce sleeve gastrectomy-induced bone loss. Bone loss is an unintended consequence of an otherwise life-saving procedure, with declining bone health potentially contributing to major morbidity in those undergoing a bariatric procedure. Identifying effective interventions to minimize bone loss is crucial for comprehensive treatment of patients who undergo bariatric surgery. Specific Aim 1: To determine the efficacy of zoledronic acid in preventing bone loss associated with sleeve gastrectomy. We will measure bone mineral density and bone turnover markers at baseline and 9 months. The primary outcome is change in bone mineral density as measured by Dual-energy x-ray absorptiometry. Secondary outcomes are change in bone mineral density as measured by Quantitative Computed Tomography and change in the serum bone turnover markers, urinary collagen type 1 cross-linked N-telopeptide (a bone formation marker), serum type 1 procollagen N-terminal (bone resorption marker), sclerostin, and osteocalcin. Specific Aim 2: To evaluate the feasibility of this trial in those who have undergone sleeve gastrectomy surgery. We will assess the feasibility of the intervention by documenting adverse events and compliance rates at each study time point.

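### With the plan's own inputs, 10 per group gives about 51–56% power for the two-group comparison, not the stated 80%

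*Combined protocol and SAP*

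**What the plan says.** The power statement is one sentence in the Statistical Analysis section. It begins "A sample size of 10 per group achieves 80% power to detect a difference of -0.02 (correlation coefficient"), sets the contrast as lying "between the null hypothesis correlation of 0.0 and the alternative hypothesis correlation of 0.02", gives an estimated standard deviation of 0.02 and a significance level of 0.05, and ends "using a two-sided Wilcoxon test, assuming that the actual distribution is normal".

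The same section enrols 30 participants, 15 randomized to each arm, and aims for 10 completers per arm. It describes the analysis of bone outcomes as follows: "Secondary analyses will examine change in bone metrics between groups assessed by a Students t-test". It also says that "all analyses are considered exploratory rather than confirmatory", that "The primary outcome of feasibility will be based on retention of participants at follow-up visits", and that "Data gathered from this study will be used to complete sample size and power calculations for a larger randomized controlled trial".

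The Summary differs on two points. It states that "The primary outcome is change in bone mineral density as measured by Dual-energy x-ray absorptiometry", and it has 20 participants randomized rather than 30.

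**The concern.** A difference of 0.02 with an SD of 0.02 is a standardised effect of 1.0. Ten per group is too few for 80% power at that effect in a two-group comparison, so the figure looked wrong at once.

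The wording adds to the doubt:

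- The effect is called a correlation but is given a standard deviation, which suits a mean difference.
- There is one null value and one alternative value, which suits a one-sample test rather than two arms.
- The power is for a Wilcoxon test, while the bone outcomes are to be compared by t-test.
- No outcome, skeletal site or unit is attached to 0.02, although the Methods plan bone density at several sites.
- The plan does not say whether the SD is of change or of a single measurement.
- The minus sign on the difference is unexplained. It is consistent only as null minus alternative, and it does not affect two-sided power.

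The Summary makes DXA bone density change the primary outcome. A reader who trusts the 80% would take a non-significant result as fairly good evidence against a difference of 0.02. The trial is also meant to supply the power calculation for a larger one. If the same formula were reused there, that trial would be too small for its comparison.

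**Working it through.** **Inputs (Statistical Analysis section).** n = 10 per group; difference δ = 0.02 in absolute value; SD σ = 0.02; two-sided α = 0.05. Standardised effect d = 0.02 / 0.02 = 1.0.

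**Assumptions.** The word correlation is a mislabel for a mean difference: read literally, a correlation of 0.02 has about 5% power with 10 or 20 people. The SD of 0.02 is the SD of change within each group.

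**Step 1: reproduce the 80%.** Treat it as a one-sample (within-group) test of mean change against zero with n = 10. The noncentrality is d√n = √10 = 3.16, with 9 degrees of freedom and critical t = 2.262. Power is 80.3%. The exact signed-rank test under normality, by simulation, gives about 79%. So the 80% is approximately right for change from zero in 10 people.

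**Step 2: the planned two-group comparison.** The noncentrality is d√(n/2), with 2n − 2 degrees of freedom. At n = 10 it is √5 = 2.236, with critical t = 2.101. Rank-sum power is simulated on normal data with exact critical values.

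| Completers per group | Two-sample t | Exact rank-sum |
|---|---|---|
| 10 | 56.2% | 51.2% |
| 15 | 75.3% | 71.6% |
| 17 | 80.7% | 78.3% |
| 18 | – | 80.3% |

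Other two-group versions at 10 per group also miss 80%: the normal approximation gives 60.9%, and a one-sided t-test at 0.05 gives 69.4%.

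**Step 3: what the sample size does deliver.** The effect detectable with 80% power (t) is d = 1.325 at 10 per group and 1.060 at 15. Multiplied by 0.02, these are differences of 0.0265 and 0.0212. The expected 95% CI half-width is about t × σ × √(2/n):

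- 10 per group: 2.101 × 0.02 × √0.2 = 0.0188
- 15 per group: 2.048 × 0.02 × √(2/15) = 0.0150

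**Step 4: sensitivity to the SD (t-test, 10 per group, difference 0.02).**

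| SD of change | 0.015 | 0.0175 | 0.02 | 0.025 | 0.03 |
|---|---|---|---|---|---|
| Power | 80.5% | 67.6% | 56.2% | 39.5% | 29.2% |

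If 0.02 is instead the SD at a single time point, the SD of change is 0.02 × √(2(1 − ρ)), where ρ is the correlation between baseline and follow-up. The documents do not give ρ.

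| ρ | 0 | 0.3 | 0.5 | 0.7 | 0.8 | 0.9 |
|---|---|---|---|---|---|---|
| Power | 32% | 43% | 56% | 78% | 92% | over 99% |

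Power reaches 80% at ρ of about 0.72.

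**The case against.** The strongest reply is that the plan never says what kind of SD 0.02 is. If it is the SD of a single measurement and repeat measurements correlate at about 0.72 or more, 80% is met or exceeded. The Methods have each participant rescanned on the same scanner with identical settings, so a high correlation cannot be ruled out. This stands as a limit on certainty: the 51–56% is conditional on 0.02 being the SD of change. It does not rescue the sentence, which states neither that reading nor any correlation.

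Second, the one-sample explanation is inference. The Wilcoxon test the sentence names gives about 79% on that reading, and only the t-test gives 80.3%. That is fair, and the cause should be called probable. The shortfall for the two-group comparison does not depend on it. Nor does a within-group reading help, because power for change within one arm says nothing about the comparison with placebo.

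Third, the stakes are low. The section calls every analysis exploratory, makes feasibility primary, and does not say that the completer goal was derived from the power figure. It says that this trial's data will feed the later calculation, not that this formula will be reused. All of that stands and limits the severity. Even so, the plan chose to state a power figure, and its Summary gives bone density primary status.

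Finally, the Wilcoxon and t-test mismatch moves power by only about five points, and the conflict between 20 and 30 randomized is a separate matter. Neither adds weight to the power finding.

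**Conclusion.** The concern holds. Taking 0.02 as the per-group SD of change, 10 completers per group give 56% power by t-test or about 51% by exact rank-sum test, against 80% stated. The chance of missing a true difference of 0.02 is therefore 44–49%, not 20%. Full retention of 15 per group would still leave power at 75% or 72%.

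The arithmetic is certain given that reading of the SD. The reading itself is an assumption that the sponsor must confirm. The sentence should be corrected, but the feasibility aim is unaffected and the design need not change.

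**What to change.** Replace the power sentence, once the sponsor has confirmed the outcome, site, unit and type of SD. If 0.02 is the SD of change, suitable text would be:

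> Assuming a per-group SD of change in [outcome, site, unit] of 0.02, 10 completers per group give 56% power (two-sample t-test, two-sided 0.05) for a between-group difference of 0.02. Power of 80% is reached at a difference of 0.0265. The expected 95% confidence interval half-width is about 0.019. These analyses are exploratory.

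If the SD is of another kind, recompute all of these except the 0.02 difference, and state the baseline to follow-up correlation used. Remove both references to correlation, and name the same test in the power statement and the analysis.

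Separately, reconcile the 20 randomized in the Summary with the 15 + 15 in the Statistical Analysis section. The 20 equals the completer goal (2 × 10) and is probably that, but the sponsor should confirm.

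The cost is wording only, with no extra participants. The one drawback is a less favourable stated power.

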## Methods

Enrolled participants will have blood drawn from the to evaluate menopausal status in those < 60 years old. Study personnel will also collect and store serum at 80 degrees Celsius, for assay of bone turnover markers and metabolic regulator proteins at a later date. Analysis of bone formation markers including procollagen Type 1 N-TerminalPropeptide (P1NP) and bone resorption marker N-Terminal Telopeptide of Type 1 Collagen (CTX) will be performed via commercially available ELISA by our laboratory. Participants will complete three surveys at baseline. The first, the Human Activity Profile (HAP), is a 94-question physical activity survey used to assess routine physical activity. The second, the Knee Injury and Osteoarthritis Outcome Score (KOOS), will assess overall knee pain, function, and knee-associated problems. Participants will also complete a modified National Osteoporosis Foundation Calcium Intake Estimate to collect dietary calcium habits. Participants will then be asked to perform three tasks relating to muscle function and gait speed: hand grip test, repeated chair stands, and a four-meter gait speed test. Participants will be measured on a standard scale for weight and have their waist circumference measured by study personnel.

Participants will obtain dual energy x-ray absorptiometry (DXA) scan or bone densitometry scan and a computed tomography (CT) scan at baseline. Bone density measurement (BDM) of the bilateral hips, spine, radius, proximal tibia as well as body composition will be measured by DXA. A CT scan of the spine and hip will be completed using the Mindway Phantom to assess bone density and bone structure, as

well as abdominal composition. CT scans will be de-identified and transferred to Wake Forest University to complete analyses of the CT scans.

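### The Summary makes change in DXA bone density the primary outcome, while the Statistical Analysis section makes feasibility primary and bone change secondary; nothing reconciles the two

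*Combined protocol and SAP*

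**What the plan says.** The Summary states that the study's "primary goal is to investigate whether bisphosphonate therapies are able to combat bone loss". Under Specific Aim 1 it says "The primary outcome is change in bone mineral density as measured by Dual-energy x-ray absorptiometry". It lists BMD by quantitative CT and the turnover markers as secondary. Feasibility comes second: "Specific Aim 2: To evaluate the feasibility of this trial in those who have undergone sleeve gastrectomy surgery", assessed there through adverse events and compliance.

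The Statistical Analysis section reverses the order. It says "The primary outcome of feasibility will be based on retention of participants at follow-up visits", adds a description of infusion tolerance, and continues: "Secondary analyses will examine change in bone metrics between groups assessed by a Students t-test". It also states that "all analyses are considered exploratory rather than confirmatory".

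The only power statement is in the same section: "A sample size of 10 per group achieves 80% power to detect a difference of -0.02 (correlation coefficient"), with an SD of 0.02, a two-sided 0.05 level and a Wilcoxon test. It names no outcome.

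On DXA sites, Methods says for baseline: "Bone density measurement (BDM) of the bilateral hips, spine, radius, proximal tibia as well as body composition will be measured by DXA". For follow-up, Methods lists hip, L1-L4, knee and radius. No site is designated as the one that counts.

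**The concern.** A trial report has to present one result as its main one. Here the document supports either of two. If the bone result is favourable, the Summary allows it to be headlined. If it is not, the Statistical Analysis section allows retention and tolerance to be headlined and the bone result to be reported as secondary. A reader of the eventual paper could not tell which was fixed in advance.

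Choosing BMD would only move the problem, because several DXA sites qualify and the same freedom returns among them. Choosing feasibility would leave a power statement that does not fit the primary outcome, since a difference with an SD suits a continuous measure and not retention or tolerance.

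**Working it through.** **1. The two sections side by side.** No arithmetic is needed for the contradiction itself.

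| | Summary | Statistical Analysis |
|---|---|---|
| Primary outcome | Change in BMD by DXA | Feasibility (retention, infusion tolerance) |
| Place of bone change | Primary (DXA); secondary (CT, markers) | Secondary analyses, t-test |
| Place of feasibility | Specific Aim 2 | Primary |
| How feasibility is measured | Adverse events, compliance | Retention, tolerance |

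The Purpose section gives a third version of Aim 2, safety and tolerance. All of this is current text, and none of it declares co-primary outcomes.

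**2. The power statement, if BMD is the primary outcome.** Inputs from Statistical Analysis: 10 per group, difference 0.02, SD 0.02, two-sided 0.05. The section calls 0.02 a correlation but also gives it an SD. I read it as a difference in means, so the standardised effect is 0.02/0.02 = 1. The planned analysis is a t-test and the power statement uses Wilcoxon, so both were checked.

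- Stated power: 80%.
- Normal approximation: 1 × √(10/2) = 2.236; Φ(2.236 − 1.960) = Φ(0.276) = 60.9%.
- Two-sample t-test (noncentrality 2.236, 18 df): 56.2%.
- Wilcoxon rank-sum, normal data, 20,000 simulated trials: about 51%.
- t-test with all 15 per arm retained: 75.3%.
- Completers per group needed for 80%: about 17 (t-test) or 18 (Wilcoxon).

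The stated figure does match a one-sample test with n = 10: 80.3% by t-test and about 78.5% by signed-rank (simulated). That may be where it came from, but the document does not say. Read literally as a correlation of 0.02, the power is about 5%.

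**3. Choice of site, if BMD is the primary outcome.** I count four regions: hip, spine, radius, and knee/proximal tibia. Treating the baseline proximal tibia and the follow-up knee as one region is my inference. Each region is compared by a two-sided t-test, 10 per group, with no true effect. The 0.05 level is taken from the power statement, its only appearance.

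- Independent regions: 1 − 0.95⁴ = 18.5%.
- Fully correlated regions: 5%.
- Simulation with equal correlation (200,000 trials each): 17.4% at 0.3, 15.8% at 0.5, 13.3% at 0.7, 9.6% at 0.9.

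The document gives no correlation, so this is a range. Counting each hip and each vertebra separately would add candidates.

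**4. Retention, if feasibility is the primary outcome.** If the goal of 20 completers out of 30 is met exactly, retention is 66.7%, with an exact 95% interval of 47.2% to 82.7%.

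**5. Imaging time.** Methods puts the follow-up visit nine months after surgery and the DXA one month after that visit: 9 + 1 = about 10 months. The Summary and Statistical Analysis say 9 months. The CT sentence appears to say the same as the DXA sentence but is unclear.

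**The case against.** The best defence has two parts. First, the phrase in Statistical Analysis may mean only the main measure for the feasibility aim, leaving BMD as the trial's primary outcome. The wording allows this, but the same paragraph goes on to place change in bone metrics under secondary analyses, and the Summary lists DXA BMD apart from its secondary outcomes. The conflict survives.

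Second, this is a small pilot whose analyses are all declared exploratory. Feasibility is to be described and not tested, so choosing between it and BMD is not choosing between two p-values. This part stands and limits the harm. It does not say which outcome is primary.

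A reader might infer that the contradiction itself raises the false-positive rate to as much as 18.5%. It does not. That figure concerns choice among DXA sites, arises only if BMD is kept, and needs independent skeletal sites within a person, which is implausible. A reader might also infer that the sponsor intends to switch outcomes, and nothing in the document suggests that. Nor does the month's difference in imaging suggest bias between arms, since the schedule is the same in both.

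**Conclusion.** The contradiction is real and should be resolved before results are known. Two different primary outcomes are stated, each is demoted in the other section, and nothing reconciles them. The consequence is freedom to choose the emphasis afterwards. No confirmatory error rate is at issue, because no confirmatory claim is planned.

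Two findings are conditional on keeping BMD as primary. No DXA site is named, which gives a 5% to 18.5% chance of at least one p<0.05 among four regions under no effect, depending on an assumed correlation. And the 80% power claim is not supported for a two-group comparison with 10 per group: it is about 56% or 51%, assuming normal data and that 0.02 is a difference in means. The contradiction does not depend on either figure.

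The imaging label is a separate, minor matter. It matters because the 9-month estimates are meant for planning the larger trial.

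**What to change.** Before results are known, designate one primary outcome, state it in the same words in the Summary and in Statistical Analysis, and list the other as secondary. The choice is the sponsor's.

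**If BMD is primary:**
- Suggested wording: *Primary outcome: areal BMD by DXA at [one named site], change from baseline to [time after surgery].* List the other sites and feasibility as secondary.
- State that the power statement refers to this outcome, drop the correlation wording, and restate the power as about 56% (t-test) or 51% (Wilcoxon rank-sum), naming the test that will be used.

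**If feasibility is primary:**
- Suggested wording: *Primary outcome: retention, the proportion of randomised participants who complete [named follow-up visit]. Infusion tolerance is reported descriptively.*
- Use one definition of feasibility in the Summary and Statistical Analysis, and bring Aim 2 in the Purpose section into line.
- Move DXA BMD to the secondary outcomes in the Summary, and say that the power statement does not refer to the primary outcome.

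**Separately:** reconcile the follow-up imaging time across the Summary, Methods and Statistical Analysis.

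**Cost:** a text amendment, with no new visits or measurements. The exception is if the sponsor keeps BMD and also wants a genuine 80% power. That needs about 17 completers per group by t-test; at the planned completion of 10/15, 17 ÷ (10/15) = 25.5, or 26 randomised per group. For an exploratory pilot, restating the power honestly is enough.

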Participants will be contacted via text message, email or phone call 24-hours and 2-months following their infusion to collect and address any adverse events/reactions/concerns they may have. The contact will include a link to a RedCap survey to self-report adverse events. If contacted via phone, study personnel will complete the adverse events form with the participant. Participants will be contacted up to 3 times, with at least 24 hours between contact in the case of non-responders.

Nine months post-bariatric surgery, participants will have a follow-up visit. Participants will be measured on a standard scale for weight and have their waist circumference measured. Participants will have blood drawn and serum will be stored at 80 degrees Celsius, for assay of bone turnover markers and metabolic regulator proteins at a later date. Analysis of bone formation markers including procollagen Type 1 N-TerminalPropeptide(P1NP) and bone resorption marker N-Terminal Telopeptide of Type 1 Collagen (CTX) will be performed via commercially available ELISA by our laboratory. Participants will complete three surveys: the Human Activity Profile (HAP), is a 94-question physical activity survey used to assess routine physical activity; the Knee Injury and Osteoarthritis Outcome Score (KOOS), will assess overall knee pain, function, and knee-associated problems; and a modified National Osteoporosis Foundation Calcium Intake Estimate to collect dietary calcium habits. Participants will complete a hand grip test, repeated chair stands, and a 4-meter gait speed test. The National Osteoporosis Foundation Calcium Intake Estimate will be used post-operatively to gather data about calcium intake from diet.

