A whole body DXA scan will be obtained one month after follow-up visit to assess body composition and bone mineral density (BMD) of the hip, lumbar vertebrae (L1-L4), knee and radius. To minimize variability between baseline and follow-up scans, each participant will be scanned on the exact same DXA scanner with identical scan parameters for each anatomic location. A real BMD (a BMD, g/cm^2) will be determined from each scan. For the femoral scan, a BMD will be calculated from the proximal femur using the scanners standard procedures. For the vertebral scan, a BMD will be calculated for each vertebral body and for all four combined using the scanners standard procedures. For the distal radius scan, a BMD will be calculated for the distal one-third of the radius using the scanners standard procedures. The DXA technologist will be blinded to treatment group for each subject. The whole body DXA also provides data on lean and fat mass, as well as distribution of these tissues. A CT scan of the lumbar vertebrae, hips and associated soft tissue will be obtained from one month after follow-up visit. To minimize variability between the baseline and follow-up scans, each participant will be scanned on the exact same CT scanner with identical scan parameters.

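### The t-test on change leaves out each turnover marker's own baseline; ANCOVA on it would probably be more precise at low to moderate correlation, at small cost and with no expected gain for BMD

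*Combined protocol and SAP*

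**What the plan says.** The Statistical Analysis section names one between-group test for the bone outcomes: "Secondary analyses will examine change in bone metrics between groups assessed by a Students t-test". No covariate is attached to it.

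Two further sentences in that section bear on adjustment. The first is "The effect of changes in relevant co-variates such as lean mass, muscle function and nutrition status on study outcomes will be assessed". The second is "Regression models will be used to control for appropriate co-variates and further explore the effect of zoledronic acid on bone after bariatric surgery". The outcome's own baseline value is named in neither, and the examples in the first are changes that occur after randomisation.

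The baseline values will exist. The Summary says "We will measure bone mineral density and bone turnover markers at baseline and 9 months" and lists change in the turnover markers among the secondary outcomes. Methods provides for serum at both visits: at baseline, "Study personnel will also collect and store serum at 80 degrees Celsius, for assay of bone turnover markers"; at 9 months, "Participants will have blood drawn and serum will be stored at 80 degrees Celsius, for assay of bone turnover markers".

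The Statistical Analysis section calls all analyses exploratory, makes feasibility primary there, and adds: "Follow-up treatment effect estimates at 9 months will be used in power calculations for future clinical trials".

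**The concern.** A change score subtracts the whole baseline value. That is the best use of the baseline only when the regression slope of follow-up on baseline is close to 1. When the slope is well below 1, as it is at moderate rho with similar SDs, subtraction over-corrects and adds noise. ANCOVA estimates the slope instead.

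With about 10 completers per arm, chance differences in mean baseline will be sizeable. At moderate rho they move a change-score estimate appreciably in any single trial, although they average out over repeated randomisations. What is at stake is the width of the marker intervals in a pilot meant to inform a larger trial, using data that will be collected anyway.

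**Working it through.** **Inputs from the documents.** 15 randomised per arm with a goal of 10 completers per arm; two-sided 0.05; difference 0.02 and SD 0.02 in the power statement (read here as BMD change, which the text does not say).

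**Assumptions.** Rho; the ratio L of follow-up SD to baseline SD; a marker effect of one SD of change; a common baseline slope in both arms. The documents give none of these.

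**1. The plan's own power figure.** The plan states 80% with 10 per group. For a two-group t-test the noncentrality is (0.02/0.02) × √(10/2) = 2.236 on 18 df, which gives 56.2%. A simulated Mann-Whitney test gives 51%. The stated figure appears only as a one-sample or paired calculation with n = 10 (t-test 80.3%). That discrepancy is a separate matter. The comparator used below is 56.2%.

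**2. Variance of ANCOVA relative to the change score.** In units of the baseline variance:
- change score: 1 + L² − 2·rho·L
- ANCOVA residual: L²(1 − rho²)
- cost of estimating the slope: (N − 3)/(N − 4) = 17/16 = 1.0625 at N = 20

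R = 1.0625 × L²(1 − rho²)/(1 + L² − 2·rho·L). With L = 1 this reduces to 1.0625 × (1 + rho)/2. ANCOVA power uses noncentrality √(5/R) on 17 df.

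| L | rho | R | ANCOVA power (t-test 56.2%) |
|---|---|---|---|
| 1 | 0.5 | 1.0625 × 0.750 = 0.797 | 65.6% |
| 1 | 0.7 | 1.0625 × 0.850 = 0.903 | 60.2% |
| 1.15 | 0.5 | 1.0625 × 0.846 = 0.899 | 60.4% |
| 1.15 | 0.7 | 1.0625 × 0.947 = 1.006 | 55.7% |
| 1.3 | 0.5 | 1.0625 × 0.912 = 0.969 | 57.2% |
| 1.3 | 0.7 | 1.0625 × 0.991 = 1.053 | 53.8% |
| 0.7 | 0.5 | 1.0625 × 0.465 = 0.494 | 85.0% |

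For equal SDs, simulation (40,000 runs per rho) gave 66% and 60% at rho 0.5 and 0.7, with type I error of 4.8 to 5.1% over all rho tried.

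**3. Interval width, equal SDs.** The 95% half-width in change-SD units is 0.940 for the t-test, against 0.842 (rho 0.5) and 0.897 (rho 0.7) for ANCOVA. These are about 10% and 5% narrower, equivalent to 10/0.797 = 12.5 and 10/0.903 = 11.1 per arm.

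**4. Break-even at 10 per arm.** As rho rises from low values, the gain runs out near 0.87 for L = 1, about 0.67 for L = 1.15 and about 0.55 for L = 1.3.

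**5. Worst case.** The change-score variance minus the ANCOVA residual variance is (1 − rho·L)², which is never negative. R therefore cannot exceed 1.0625. At that bound the noncentrality is √(5/1.0625) = 2.169 on 17 df, giving power of 53.4%, a loss of 2.8 points.

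**6. Chance imbalance, equal SDs.** One standard error of baseline difference is √(2/10) = 0.447 SD. It shifts the change-score estimate by (1 − rho) × 0.447/√(2(1 − rho)), which is 0.22 change SD at rho 0.5 and 0.17 at rho 0.7. The ANCOVA estimate shifts by zero on average.

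**7. If all 15 per arm are retained, equal SDs.** The t-test has 75.3% power; ANCOVA has 84.9% (rho 0.5) or 80.2% (rho 0.7). Break-even is near rho 0.92.

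**8. BMD.** With a change SD of 0.02, equal SDs and an assumed between-person SD of 0.08 to 0.15 g/cm², rho = 1 − 0.02²/(2·SD²), which is 0.97 to 0.99. R is then 1.05 to 1.06. At rho 0.95 to 0.98, ANCOVA power is 54.5 to 53.8%, slightly below the t-test.

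**The case against.** The strongest reply is that the plan already provides for adjustment. Read whole, it has an unadjusted t-test followed by regression models for the effect of zoledronic acid, and baseline is an obvious candidate covariate. A reader might infer that the plan makes no baseline adjustment at all; the text does not support that. What stands is that the named between-group test is unadjusted and that the regression sentence does not name the outcome's baseline.

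The second reply is that the gain rests on quantities the documents do not give. This is right, and equal SDs should not be presumed. The Background describes raised turnover markers after surgery and a drug that inhibits bone resorption, so the marker distribution may change over time and differ by arm. The 0.87 break-even is therefore not a general threshold: a 15% rise in SD removes the gain at rho 0.7. The dependence runs both ways, since a smaller follow-up SD enlarges the gain.

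Third, the documents do not say that marker estimates in particular will feed the later power calculations. The only effect and SD given are read here as BMD, where ANCOVA is not expected to help. The argument from future use is correspondingly weaker for the markers.

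A reader might also infer that the covariate changes named in the plan bias the treatment effect. The documents do not say that those changes enter the treatment-effect model, or that an estimate adjusted for them goes forward, so no bias is shown.

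**Conclusion.** The point holds as a minor improvement in efficiency, confined to the turnover markers. The planned t-test is not wrong. ANCOVA on each marker's own baseline is likely to be more precise if rho is low to moderate. Under the equal-SD assumption the gain at 10 per arm is about 9 power points at rho 0.5 and 4 at rho 0.7. Across the SD ratios examined (0.7 to 1.3), it ranges from much larger to a loss of 2 to 3 points. That loss is the limit when both arms share a slope.

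Confidence that the baseline is not named is high; confidence in the size of the gain is low. No defect is claimed for BMD, and that exclusion itself assumes similar SDs at the two visits and a 0.02 SD of change. Because the analyses are exploratory and the markers secondary, nothing in the trial's main conclusions depends on this.

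**What to change.** In the Statistical Analysis section, state that the between-group comparison for each turnover marker is an ANCOVA of the 9-month value (or change) on treatment group and that marker's baseline value, reported with a 95% CI. The treatment estimate is the same whichever of the two is the outcome. Keep the t-test on change for BMD.

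For every bone metric, report the baseline SD, follow-up SD and rho, so that the larger trial can judge from data whether baseline adjustment pays. Write the choice of model down in advance rather than selecting it after rho is known.

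The cost is SAP wording only, with no new visits, samples or assays. Statistically it is one degree of freedom (17 rather than 18 with 20 completers) and at most about 6% more variance for a marker whose slope proves to be close to 1.
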